4.1	Wear time and compliance	Record the subject's wearing time and comfortable wearing time. Subjects must have worn lenses for at least five continuous 8-hour periods during the dispensing period and for at least 1 hour prior to attending this visit.			
4.2	Collect unworn lenses	Collect any unworn study lenses that were dispensed at the previous visit.			
4.3	Review medical history and concomitant medications	Record any changes to the subject's medical history (including adverse events) or concomitant medications.			
4.4	Subject reported ocular symptoms	Record any subject reported ocular symptoms in response to a verbal open-ended symptoms questionnaire.			
4.5	Follow-up PRO questionnaire	Subjects will complete a PRO questionnaire to assess their experience with the study lenses.			
4.6	Entrance visual acuity	Record the entrance Snellen VA for each eye while wearing the study lenses.			
4.7	Measure monocular distance high luminance of contrast (HLHC) visual acuity using ETDRS chart 4 meters. Measure each eye using the charts shown in the table below:			ETDRS cha	rts
		Condition	HL	HC	Ĩ
		Room illumination	> 40	0 lux	
		Chart luminance	120 - 20	00 cd/m ²	
		Eye	OD	OS	
		Charts	HC-1	HC-3	
		HC-2 HC-4			
4.0	T:-1	Recorded letter-by-letter results into EDC.			
4.8	Toric lens orientation	Record the toric lens orientation for each eye to the nearest degree.			

Visit 4: Follow-Up #2			
Step	Procedure	Details	
4.9	Additional sample of toric lens orientation (1)	Instruct the subject to leave the consulting room and walk around for at least 2 minutes. Upon their return, measure and record the toric lens orientation to the nearest degree in each eye.	
4.10	Additional sample of toric lens orientation (2)	Repeat the previous step once again.	
4.11	Lens removal	Remove and place both lenses into a lens case with saline solution. Do not discard the lenses until after biomicroscopy has been completed.	
4.12	Biomicroscopy	The FDA Slit Lamp Classification Scale will be used to grade findings. If any slit lamp finding is graded as 3 or worse, an adverse event will be recorded, and the subject will be monitored as per the guidelines given in section 13. Should the clearance of the fluorescein need to be expedited, preservative free rewetting drops or artificial tears may be instilled. Study lenses may be discarded if there is no reason to store them following biomicroscopy.	

FINAL EVALUATION

The final evaluation will ordinarily take place immediately following the last scheduled follow-up visit per the study protocol. It may also take place at any point the subject discontinues the study or is terminated from the study.

Final Evaluation			
Step	Procedure	Details	
F.1	Subject Disposition	Indicate if the subject completed the study successfully. If the subject is discontinued from the study, indicate the reason.	
F.2 Exit Refraction Perform bare-eye subject refraction with a phoropy corrected distance visual the nearest letter. Note: This step is not not refraction.		Perform bare-eye subjective spherocylindrical refraction with a phoropter and record the best-corrected distance visual acuity (OD and OS) to the nearest letter. Note: This step is not necessary if the subject was exited due to screen failure.	

Final Evaluation			
Step	Procedure	Details	
F.3	Exit Slit Lamp Biomicroscopy (for subjects that are	FDA Slit Lamp Classification Scale will be used to grade the findings.	
	discontinued early)	If the clearance of the fluorescein needs to be expedited, preservative-free rewetting drops or saline may be instilled. This step is not necessary if the subject was exited due to screen failure.	
		Note : This step is not necessary if the subject was exited due to screen failure, or if biomicroscopy was performed as part of the final follow-up visit procedures (i.e., immediately prior to the final evaluation).	

7.3. Unscheduled Visits

If, during the investigation, a subject requires an unscheduled visit to the clinical site, the following information will be collected, as appropriate:

- Chief complaint prompting the visit. If the reason is an adverse event, the applicable eCRF for the adverse event must be completed and subject record completed as appropriate.
- Date and time of the visit and all procedures completed at the unscheduled visit.
- Review of adverse event and concomitant medications.
- Documentation of any test article dispensed or collected from the subject, if applicable.
- Slit lamp findings (using the Slit Lamp Classification Scale).

If the Investigator withdraws a subject from the study, the final study visit case report forms must be completed indicating the reason(s) why the subject was withdrawn. The subject record must be completed documenting the date and primary reason for withdrawal and the study CRA notified.

Any ocular and non-ocular Adverse Events that are ongoing at the time of the study visit will be followed by the Investigator, within licensure, until they have resolved, returned to pretreatment status, stabilized, or been satisfactorily explained. If further treatment i.e., beyond licensure is required, the subject will be referred to the appropriate health care provider.

The following information will be collected during an unscheduled visit.

Unscheduled Visit			
Step	Procedure	Details	
U.1	Reason for unscheduled visit	Indicate if the only reason for the visit is that the subject requires additional test articles. If the reason is other than resupply of previously dispensed lenses, specify the reason for the visit.	

Unscheduled Visit			
Step	Procedure	Details	
U.2	Chief Complaints (if applicable)	Record the subject's chief complaints for reasons for the unscheduled visit.	
U.3	Adverse Events and Concomitant Medications Review (if applicable)	Review any changes to the subject's medical history or concomitant medications from the previous study visit. Record any changes, and any adverse events.	
U.4	Entrance VA (if applicable)	Record the entrance distance visual acuity (OD, OS) to the nearest letter.	
U.5	Subjective Sphero- cylindrical Refraction (if applicable)	Perform bare-eye subjective spherocylindrical refraction with a phoropter (adopt the maximum plus to maximum visual acuity (MPMVA) approach and use the duo-chrome test for binocular balancing) and record the best corrected distance visual acuity to the nearest letter (OD, OS).	
U.6	Slit Lamp Biomicroscopy (if applicable)	FDA Slit Lamp Classification Scale will be used to grade the findings. If the clearance of the fluorescein needs to be expedited, preservative-free rewetting drops may be instilled.	
U.7	Dispensing (if applicable)	If the subject requires additional lenses to complete the wear period and is eligible to do so, provide additional lenses per the dispensing instructions given in the detailed study procedures.	
U.8	Exit Visual Acuity (if applicable)	Record the subject's exit distance visual acuity (OD, OS) to the nearest letter.	

NOTE: If the only reason for the unscheduled visit is that the subject requires additional test articles, only the dispensing information needs to be recorded.

7.4. Laboratory Procedures

Not applicable.

8. SUBJECTS COMPLETION/WITHDRAWAL

8.1. Completion Criteria

Subjects are considered to have completed the study if they:

- provided informed consent.
- they are eligible.
- have not withdrawn/discontinued from the study for any reason described in section 8.2.

- completed all visits through the final visit (visit 4).
- If all visits were completed but an additional visit is considered necessary for subject care, follow the requirements for unscheduled visits in section 7.3.

8.2. Withdrawal/Discontinuation from the Study

A subject will be withdrawn from the study for any of the following reasons:

- Subject withdrawal of consent.
- Subject not compliant to protocol.
- Subject lost to follow-up.
- Subject no longer meets eligibility criteria (e.g. the subject becomes pregnant).
- Subject develops significant or serious adverse events necessitating discontinuation of study lens wear.
- Subjects who have experienced a Corneal Infiltrative Event (CIE).
- Investigator's clinical judgment regarding the subject safety reasons (that it is in the best interest of the subject to stop treatment).
- Subject misses any study visits.
- Subject not compliant with study lens wear schedule.
- Subject not successfully dispensed due to lack of efficacy and safety including poor vision, poor comfort or unacceptable fit.

For discontinued subjects, the Investigator will:

- Complete the current visit (scheduled or unscheduled).
- Complete the Final Evaluation, indicating the reason that the subject was discontinued from the study.
- Record the spherocylindrical refraction with best corrected distance visual acuity.
- Collect used test article(s) (worn or brought to the visit) from the subject and discard them, unless otherwise stated in section 7.2.
- Collect all unused test article(s) from the subject.
- Make arrangements for subject care, if needed, due to their study participation.

Additional subjects may be enrolled if a subject discontinues from the study prematurely.

In cases where a subject is lost to follow-up, every possible effort must be made to contact the subject and determine the reason for discontinuation/withdrawal. The measures taken to follow up must be documented including two written attempts and a certified letter (or equivalent) as the final attempt.

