4.2. Study Design Rationale

A 2×2 crossover study design was chosen to allow each subject to act as their own active control. A washout period will be included to mitigate any carryover effects.

The prescribed wear schedule (7±2 days, minimum of 8 hours per day, minimum of 5 days per week) was chosen as this is representative of a typical wear schedule for contact lens wearers.

Slit lamp biomicroscopy was selected as the method for assessing ocular health, on the basis that it is the most commonly used instrument for comprehensive examination of the anterior eye. The FDA slit lamp findings classification scale was selected for grading ocular health on the basis that it is widely used and is part of the FDA regulatory guidance for contact lenses (FDA 510(k) guidance).

The investigational lenses will be fitted by optometrists who are experienced at fitting toric soft contact lenses and will be evaluated by habitual contact lens wearers in their standard wearing environment.

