2.1	Wear time and compliance	Record the subjects wearing time and comfortable wearing time. Subjects must have worn lenses for at least 8 hours on at least 5 days during the dispensing period, and for at least 1 hour prior to attending this visit.		
2.2	Collect unworn lenses	Collect any unworn study lenses that were dispensed at the previous visit.		
2.3	Review medical history and concomitant medications	Record any changes to the subject's medical history (including adverse events) or concomitant medications.		
2.4	Subject reported ocular symptoms	Record any subject reported ocular symptoms in response to a verbal open-ended symptoms questionnaire.		

		Vi	sit 2: Follow-up	#1		
Step	Procedure	Details				
2.5	Follow-up PRO	Subjects will complete a PRO questionnaire to				
	questionnaire	assess their experience with the study lenses.				
2.6	Entrance visual acuity	Record the entrance Snellen VA for each eye				
2.7	Distance ETDRS	while wearing the study lenses. Measure monocular distance high luminance high				
2	visual acuity	contrast (HLHC) visual acuity using ETDRS charts				
	100	at 4 meters.				
		Measure each eye using the charts shown in the				
		table below:				,
		Condition HLHC]	
		Room illumination		> 40	0 lux	
		Cha	rt luminance	120 - 20	00 cd/m^2	
		Eye		OD	OS	1
				HC-1	HC-3	1
		Cha	irts	HC-2	HC-4	
		Record	ed letter-by-lette	r results into	EDC.	1
2.8	Toric lens orientation	Record the toric lens orientation for each eye to				
2.9	Additional sample of		rest degree.	arra tha ann	nitina na an	
2.9	Additional sample of toric lens orientation	Instruct the subject to leave the consulting room and walk around for at least 2 minutes. Upon their return, measure and record the toric lens				
	(1)					
			tion to the near			
2.10	Additional sample of toric lens orientation (2)	Repeat the previous step once again.				
2.11	Lens removal	Remove and place both lenses into a lens case				
		with saline solution.				
		Do not discard the lenses until after				
2.12	Biomicroscopy		oscopy has been			he
2.12	Бюнистовсору	The FDA Slit Lamp Classification Scale will be used to grade findings. If any slit lamp finding is				
		graded as 3 or worse, the subject must be				
		A 100 CO OF THE REAL PROPERTY	inued, an adver			Part Delivers
		and the subject will be monitored as per the guidelines given in section 13. Should the clearance of the fluorescein need to be expedited, preservative-free rewetting drops or artificial tears may be instilled.				the
						he

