		Study lenses may be discarded if there is no				
2.13	Evit vicual acuity	reason to store them following biomicroscopy. Record the exit monocular distance Snellen visual				
2.13	Exit visual acuity	acuity for each eye with the subject wearing their habitual correction.				

Visit 2: Follow-up #1				
Step	Procedure	Details		
2.14	Schedule next visit	Schedule the next visit (Visit 3) to occur following a washout period of 7(±2) days (counting the day of this visit as day 0, the subject may return on day 5 through 9). Subjects may wear their habitual lenses during the washout period.		

VISIT 3

Visit 3 will occur 5 to 9 days following Visit 2. Subjects may wear their habitual contact lenses to this visit.

Visit 3: Continuance				
Step	Procedure	Details		
3.1	Review medical history and concomitant medications	Record any changes to the subject's medical history or concomitant medications.		
3.2	Subject reported ocular symptoms	Record any subject reported ocular symptoms in response to a verbal open-ended symptoms questionnaire.		
3.3	Entrance visual acuity	Record the entrance distance Snellen visual acuity for OD and OS with the subject wearing their habitual correction.		
3.4	Remove habitual lenses (if worn)	If worn, the subject's habitual contact lenses will be removed. Lenses may be stored in a lens case, if required.		
3.5	Biomicroscopy	The FDA Slit Lamp Classification Scale will be used to grade findings. If any slit lamp finding is graded as 3 or worse, the subject must be discontinued, an adverse event will be recorded and the subject will be monitored as per the guidelines given in section 13. Should the clearance of the fluorescein need to be available preservative free rewetting drops or		
3.6	Continuance	expedited, preservative free rewetting drops or artificial tears may be instilled. Verify that the subject is eligible to continue in the		
2.0		study.		

Visit 3: Lens Fitting #2

The steps followed will be the same as those listed under Visit 1: Lens fitting #1.

VISIT 4

Visit 4 will occur 5 to 9 days following Visit 3. Subjects must present to this visit wearing the study lenses in both eyes, and lenses must have been worn for at least 1 hour prior to the visit. Subjects should bring their own habitual spectacles or contact lenses to this visit to wear following study lens removal.

Visit 4: Follow-Up #2					
Step	Procedure	Details			

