Significant Adverse Events – are defined as events that are symptomatic and warrant discontinuation (temporary or permanent) of the contact lens wear

Diagnoses and conditions that are considered Ocular Significant Adverse Events include, but not limited to the following:

- Contact Lens Induced Peripheral Ulcer (CLPU)
- Significant Infiltrative Events (SIE)
- Superior Epithelial Arcuate Lesions (SEALs)
- Any Temporary Loss of > 2 Lines of BSCVA
- Other grade 3 or higher corneal findings, such as abrasions or edema
- Non-contact lens related corneal events e.g. Epidemic Keratoconjunctivitis (EKC)
- Asymptomatic Corneal Scar
- Any corneal event which necessitates temporary lens discontinuation > 2 weeks

Non-Significant Adverse Events – are defined as those events that are usually asymptomatic and usually do not warrant discontinuation of contact lens wear but may cause a reduction in wear time. However, the Investigator may choose to prescribe treatment as a precautionary measure.

Diagnoses and conditions that are considered Ocular Non-Significant Adverse Events include, but not limited to the following:

- Non-significant Infiltrative Event (NSIE)
- Contact Lens Papillary Conjunctivitis (CLPC)
- Superficial Punctate Keratitis (SPK)
- Conjunctivitis: Bacterial, Viral, Allergic

- Blepharitis
- Meibomianitis
- Contact Dermatitis
- Localized Allergic Reactions
- Any corneal event not explicitly defined as serious or significant adverse event, which necessitates temporary lens discontinuation < 2 weeks

Adverse Device Effect (ADE) – An ADE is an "adverse event related to the use of an investigational medical device."

NOTE 1: This definition includes adverse events resulting from insufficient or inadequate instructions for use, deployment, implantation, installation, or operation, or any malfunction of the investigational medical device.

NOTE 2: This definition includes any event resulting from use error or from intentional misuse of the investigational medical device.¹

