Upon discovery of an AE that is deemed 'possibly related' or 'related' to the test article or study procedures (whether related to the visual system or not), an AE review form must be completed. Additional dated and initialed entries should be made at follow-up evaluations. Separate forms must be completed for each eye if the AE is bilateral.

In addition, if an infiltrate(s) is present, he/she will complete the Corneal Infiltrate Assessment eCRF. Where necessary, a culture of the corneal lesion will be collected to determine if the infection is microbial in nature. If cultures are collected, the date of culture collection and laboratory utilized will be recorded.

Changes in the severity of an AE shall be documented to allow an assessment of the duration of the event at each level of intensity to be performed. Adverse events characterized as intermittent require documentation of the onset and duration of each episode. Changes in the assessment of relationship to the Test Article shall also be clearly documented.

Subjects who present with an adverse event shall be followed by the Investigator, within licensure, until all signs and symptoms have returned to pre-treatment status, stabilized, or been satisfactorily resolved. If further treatment beyond licensure is required, the patient will be referred to the appropriate health care provider. The Investigator will use his/her clinical judgment as to whether a subject reporting with an adverse event will continue in the study. If a subject is discontinued from the study, it will be the responsibility of the Investigator to record the reason for discontinuation. The Investigator will also document the adverse event appropriately and complete the Adverse Event eCRF. Any subjects with ongoing adverse events related to the test article, study treatment or study procedures, as of the final study visit date, should be followed to resolution of the adverse event or until referral to an appropriate health care provider, as recommended by the Investigator. Non-ocular adverse events that are not related to the test article, study treatment, or study procedures may be recorded as "ongoing" without further follow-up.

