14.5. Primary Analysis

Descriptive summary tables by Lens Type (DT1fA vs. P1fA) for the following safety and efficacy endpoints will be provided.

• Incidence of grade 3 or higher biomicroscopy findings using the FDA grading scale following a 7(±2) day wear period

14.6. *2.30*Secondary Analysis

Not applicable.

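### The by-lens primary table pools an unselected first period with a second period seen only in first-lens non-reactors; add a period and sequence breakdown

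*Combined protocol and SAP*

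**What the plan says.** The protocol (sections 4.1 and 5.1) describes a 2×2 crossover with 1:1 allocation to two sequences. The reason given in section 4.2 is: "A 2×2 crossover study design was chosen to allow each subject to act as their own active control".

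The primary endpoint (section 2.2) is the incidence of grade 3 or higher biomicroscopy findings after each 7±2 day wear period. Several passages bear on what happens once a subject has such a finding:

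- **Section 7.2, step 2.12 (Visit 2, end of the first wear period):** for any finding "graded as 3 or worse, the subject must be" discontinued.
- **Section 7.2, step 3.5 (Visit 3, before the second fitting):** "If any slit lamp finding is graded as 3 or worse, the subject must be discontinued, an adverse event will be recorded".
- **Section 8.2:** withdrawal from the study after a corneal infiltrative event, and also where "Subject develops significant or serious adverse events necessitating discontinuation of study lens wear".
- **Section 13.1:** significant adverse events include "Other grade 3 or higher corneal findings, such as abrasions or edema".
- **Section 13.3:** "The Investigator will use his/her clinical judgment as to whether a subject reporting with an adverse event will continue in the study".

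The analysis in section 14.5 is: "Descriptive summary tables by Lens Type (DT1fA vs. P1fA) for the following safety and efficacy endpoints will be provided". It mentions neither period nor sequence. Section 14.9 imputes nothing and reports counts of missing values. Section 14.3 defines Safety, Per-Protocol and ITT sets, but the plan does not say which one the primary table uses. No hypothesis is tested (sections 2.3 and 14.4).

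**The concern.** The event that stops a subject before the second lens is the primary endpoint itself, so this is removal on the outcome and not incidental dropout. First-period incidence comes from everyone fitted and examined. Second-period incidence comes only from those who got through the other lens without a grade 3 finding. A by-lens table without a period split averages the two.

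If a subject who reacts to one lens is more likely to react to the other, the second period has lost the subjects most at risk. Pooled incidence is then understated for both lenses. When the lenses differ, the worse lens removes more susceptible subjects ahead of the better one, so the better lens is understated proportionately more. Replacing discontinued subjects, which section 4.3 allows, does not help, because replacements also reach the second lens only by passing the first.

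The first-period comparison between lenses is randomised and free of this selection, but the plan does not call for it to be shown.

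**Working it through.** **The plan's own figure.** The only sample-size figure is 66 enrolled for 60 completers at 10% dropout. 60 × 1.10 = 66, and 60 / 0.90 = 66.7, so it reproduces to within one subject. The plan gives no event rate, within-subject correlation or bias figure, so everything below rests on assumed values shown as ranges.

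**Model.** Let the true incidences be pA and pB, and let j be the probability that a subject would react to both lenses. Take 1:1 sequences and assume that every first-period event leads to removal. Half the subjects wear A first and contribute pA. The other half wear B first; a fraction 1 − pB of them reach A, and pA − j reach it and react. Hence, in an as-observed table:

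- observed A = (2pA − j) / (2 − pB)
- observed B = (2pB − j) / (2 − pA)

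j is taken from a bivariate normal with latent correlation r.

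**Equal true rates of 5%:** observed = (0.10 − j) / 1.95.

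| r | j | Observed | Relative bias |
|---|---|---|---|
| 0 | 0.00250 | 5.0% | 0% |
| 0.3 | 0.00713 | 4.8% | −5% |
| 0.5 | 0.01219 | 4.5% | −10% |
| 0.8 | 0.02476 | 3.9% | −23% |
| 1.0 | 0.05000 | 2.6% | −49% |

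**Cross-check with the correlation φ of the two binary events.** For equal rates p, relative bias = −(1 − p)φ / (2 − p). At p = 5% and φ = 1 this is −0.95 / 1.95 = −49%, the same ceiling. At φ = 0 it is zero. If reactions to the two lenses were mutually exclusive, the bias would be slightly upward (+2.6% at p = 5%).

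**Unequal true rates of 6% and 3%** (true ratio 2.0, true difference 3.0 points):

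- r = 0.8, j = 0.01945: A = 0.10055 / 1.97 = 5.10%; B = 0.04055 / 1.94 = 2.09%. Ratio 2.4, difference 3.01 points.
- r = 1.0, j = 0.03: A = 0.09 / 1.97 = 4.57%; B = 0.03 / 1.94 = 1.55%. Ratio 2.95, difference 3.02 points.

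The ratio moves while the risk difference hardly changes.

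**Scale against sampling error.** At assumed rates of 1% to 5%, 60 subjects give 0.6 to 3 expected events per lens. The exact 95% interval for 1 of 60 is 0.04% to 8.9%. The worst-case bias (r = 1) is 0.5 points at a 1% rate and 2.4 points at 5%.

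**Period 1 alone** has 60/2 = 30 to 66/2 = 33 subjects per lens. The exact 95% upper limit for zero events is 1 − 0.025^(1/n): 11.6% at n = 30 and 6.0% at n = 60.

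**The case against.** Several points on the other side stand.

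- **The rule alone creates no bias.** Positive within-subject correlation is also needed, and the documents give none. The crossover rationale in section 4.2 suggests that responses are related, but says nothing about how strongly for a rare binary event. At a 1% rate and latent correlation 0.5 the bias is only −6%, or 0.06 points.
- **The absolute contrast between lenses survives.** The risk difference is essentially unchanged, and the plan names no ratio as its measure.
- **The rules are not uniform.** The adverse event ground in section 8.2 is conditional on having to stop lens wear, so it is not the main driver; step 2.12 is. Visit 3 follows a washout in which habitual lenses may be worn, so a step 3.5 finding is not clearly a reaction to the first study lens. Section 13.3 leaves continuation to the investigator, which does not fit the mandatory wording of steps 2.12 and 3.5.
- **Imprecision dominates.** The study is descriptive and unpowered, and sampling error is larger than the bias at plausible rates.
- **Some of the information is already collected.** Discontinuation reasons (step F.1) and missing counts (section 14.9) are recorded.

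These limit the size of the point but do not remove it. An interval would display sampling error, whereas a pooled table gives no sign of the selection. Section 14.2 says the data may be used to design later studies, so the table should say what it estimates.

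**Conclusion.** The selection is real, and neither section 14.5 nor section 14.9 addresses it. Its numerical effect is conditional on within-subject correlation: none at latent correlation 0 and, at an assumed 5% rate, about 5% to 23% relative understatement for latent correlations of 0.3 to 0.8.

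A reader might infer that the withdrawal rules make the primary table too low by about half. The documents do not support that. Half is the limit reached when exactly the same subjects react to both lenses at equal rates, and nothing in the plan indicates that. Nor can distortion of the between-lens comparison be claimed in general: the ratio is inflated, but the risk difference is not materially affected.

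The figures assume that every first-period endpoint event leads to removal, and they apply to as-observed Safety or ITT denominators. They do not carry over to the Per-Protocol set, where first-lens reactors drop out of both periods. There the relative bias for equal rates is −(1 + φ)/2, already −50% under independence.

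This is a worthwhile, inexpensive improvement to the primary table. It does not undermine the study.

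**What to change.** Leave the withdrawal rules unchanged. In section 14.5:

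1. Report grade 3 or higher incidence by lens within each period and sequence, beside the pooled table. Use subjects exposed and examined as denominators, and state the analysis set.
2. Identify the period 1 by-lens comparison as the randomised one free of this selection.
3. Label the pooled table as conditional, for its second-period part, on reaching the second lens.
4. Tabulate, by first lens worn and by reason, the subjects who never received the second lens.

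Separately, section 13.3 and steps 2.12 and 3.5 must be reconciled, so that it is clear when a first-period finding ends participation.

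The cost is some SAP wording and one descriptive table from data already collected. The downside is precision: period 1 has about 30 to 33 subjects per lens, and the wider limits shown above apply. The pooled table should therefore stay beside it.
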